The target of our study is to have 100 subjects complete the study, excluding prior pilot study data. We will run a blinded interim analysis on the primary endpoint when 25 subjects in each arm have completed treatment and follow-up, and a conditional power for detecting a significant treatment effect by the planned end of the study (100 subjects) will be determined. If this conditional power is between 50 and 80%, the sample size will be recalculated to achieve 80% conditional power following the algorithm of Chen and DeMets (2004). Otherwise, the study will continue until 100 patients have completed treatment.

Based on prior pilot study data, we anticipate the study dropout rate to be approximately 30%, from time of initial enrollment to completion of the post-treatment survey. During the prior pilot study, the dropout rate was 50% initially, and dropped to 30% during the last 8 months of enrollment, until the study was closed. Dropout rate was the same in each arm, with 5 subjects in each arm dropping out after starting treatment. Only three subjects cited adverse events (AEs) as a reason for drop out; two subjects on placebo complained of headache and dry mouth, respectively, and one subject on amitriptyline complained of sedation.

Thus, we anticipate a dropout rate during treatment of 30%, and anticipate having to enroll at least 75 subjects in order for 25 patients in each arm to complete the study by the interim analysis.

The physician may elect to discontinue study drug due to serious adverse events (SAEs) or unintended pregnancy. If a subject withdraws from treatment due to adverse events, we will ask that they continue coming in for follow-up visits and finish the remaining parts of the visits off the study drug.

The primary endpoint of the trial will be the total modified RSI at 8 weeks. The Reflux Symptom Index (RSI) has been validated by Belfasky et. al. [Belafsky PC, Postma GN, Koufman JA. Validity and reliability of the reflux symptom index (RSI). *Journal of Voice*. 2002;16:274-277]. The RSI is a questionnaire consisting of 9 statements to be ranked 0-5. We have added two additional symptoms to be assessed with the RSI, "throat pain or burning" and "pain with swallowing", which we believe are also relevant to chronic laryngeal neuropathy.

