The total modified RSI score at 8 weeks will be averaged for each group (amitriptyline vs. placebo) and differences compared between the treatment and placebo arms using analysis of covariance adjusting for baseline severity scale at an overall two-sided 0.05 level of significance across the interim and final analysis (a two-sided significance level

of 0.00306 at the interim and 0.049 at the final analysis). A Wilcoxon Rank Sum test will be used in the case that the data is found to have a non-normal distribution.

A secondary outcome will be improvement in overall symptoms (yes/no), as subjectively assessed by patients. The post treatment survey will ask both the patient and the principal investigator whether they thought the subject was on amitriptyline or placebo.

Additional secondary outcomes will be whether there are changes in scores from baseline on the Voice Handicap Index-10 after treatment [Rosen et. al. Development and Validation of the Voice Handicap Index-10. *The Laryngoscope*. 2004; 114: 1549-1556] and change in score from baseline on the Cough Severity Index (CSI).[Shembel AC et al.. Development and validation of the cough severity index: a severity index for chronic cough related to the upper airway. *Laryngoscope*. 2013;123(8):1931-6.] The VHI-10 is a 10-question scale that addresses effects on quality of life from voice disorders while the CSI is a 10-item likert scale that assesses cough symptoms. Furthermore, we will determine whether the severity of each symptom within the modified RSI has improved after treatment. This will account for questions that may be less relevant to laryngitis overall (and more specific to reflux).

Frequencies of AEs for both groups of patients and the rate of discontinuing treatment will be recorded.

The study will be stopped if any patient is permanently disabled, seriously injured, or dies in a manner that could be consistent with the drug usage. The study will be continued if said patient(s) were taking the placebo or the event is demonstrably unrelated to the subject's participation in the trial.

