An independent monitor within the otolaryngology department who is not associated with study recruitment or data analysis will also review adverse events for all subjects. The independent monitor will submit a report to the PI, who will then review these events and submit a report to the IRB. Also, if there is a concerning event or group of events, the PI will bring these to the attention of the independent monitor as they occur.

A report will be submitted to the IRB and the PI by the independent monitor at the intervals described in safety monitoring section (see section on Safety monitoring/reporting for more detail).

Analysis (efficacy and safety)

We will be using the 8 week post-treatment 11-point modified RSI score as our primary outcome. Treatments will be compared using analysis of covariance adjusting for the baseline value using a two-sided 0.05 level of significance.

We thus used the RSI to calculate our sample size. The average starting RSI for subjects with a similar type of laryngitis to what we are studying is 20.9. After treatment, the average was 12.8 (Belfasky et. al. 2002). We estimated a 20% improvement for the

placebo group, using the estimate for continuous indicators from Hróbjartsson et. al. meta-analysis of placebo effects. Thus, we predicted the final mean RSI for the placebo patients to be 16.72. The difference between the means is thus assumed to be 3.92. Dividing this mean difference by the anticipated standard deviation (10.0, using the value from Belfasky et. al. for the final RSI value post-treatment) gives an anticipated standardized effect size of 0.392. Using this for the calculation for a-priori sample size calculations (using two-sided $p < 0.05$ and a desired power level of 0.8) gives a needed sample size of 208.

In prior pilot study data, mean difference in RSI scores was +13 (increase in score post treatment) for the amitriptyline group and +16.4 in the placebo group, with standard deviations of 7.8 and 12.1, respectively. The p-value used to determine significance was 0.5 for a two-tailed unpaired t-test.

Currently, funding is available for 100 subjects to complete this study, not including subjects who completed treatment in the prior pilot study. With a dropout rate of 30%, we expect to enroll 130 subjects in order for 100 to complete treatment. With a standard deviation of 10 as per prior assumptions, we would be able to detect a mean difference of 6 by one-tailed ANOVA analysis.

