When 25 subjects in each arm (placebo and amitriptyline) have completed the study and follow-up (i.e. at least 50 subjects total), a blinded interim analysis will be performed, and conditional power for detecting a significant treatment effect by the planned end of the study (100 subjects) will be determined. If this conditional power is between 50 and 80%, the sample size will be recalculated to achieve 80% conditional power following the algorithm of Chen and DeMets (2004). Otherwise, the study will continue until 50 subjects in each arm have completed treatment.

For data analysis, we will be performing both per-protocol and multiple imputation approach analyses. Multiple imputation using the linear regression approach will be used to impute missing data, for subjects who do not complete treatment. Intention-to-treat analysis is not possible, since our outcomes are determined by the 8 week post-treatment survey, and there are no intermediate data points with regards to treatment efficacy outcomes (ie, subjects who drop out will not have any outcomes recorded).

The primary outcome measure will be the pre- and post- treatment difference in scores on the Reflux Symptom Index (RSI), with two additional questions added to assess for symptoms that may be more specific to chronic laryngeal neuropathy.

The RSI is a validated questionnaire consisting of 9 statements to be ranked 0-5. We have added two additional symptoms to be assessed to the RSI, "throat pain or burning" and "pain with swallowing", which we believe may also be relevant to chronic laryngeal neuropathy.

The modified RSI score will be averaged for each group (amitriptyline vs. placebo), and since it is a nearly continuous variable (with an expected normal distribution) and we will

be comparing the mean of the change rather than categorizing the treatment into responder and non-responders, we will also analyze it using an Analysis of Covariance or Wilcoxon Rank Sum test if determined to have a non-normal distribution.

For the modified RSI, we will also conduct a secondary analysis looking at change in severity of each symptom individually. This will account for questions that may be less relevant to laryngitis overall (and more specific to reflux).

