Secondary outcome measures will be 1) subjective percent improvement from baseline to after 8 weeks of treatment, 2) subjective report of whether symptoms are better, worse, or same after treatment, and 3) the pre- and post- treatment mean difference in scores on the Voice Handicap Index-10 (VHI-10). 4) the pre- and post- treatment mean difference in scores on the Cough Severity Index.

The VHI-10 is a 10-question scale that addresses effects on quality of life from voice disorders. By asking respondents to score symptoms on the VHI-10 scale, we expect to gain additional data on the effects of amitriptyline on improvement in voice-related issues.

The Cough Severity Index is a 10-item likert scale. which is a validated questionnaire used to quantify a patient's symptoms associated with upper airway chronic cough, and will allow us to better understand the effect of the amitriptyline intervention for chronic cough.

Subjects

Inclusion Criteria:

1. Age 18 or older and able to consent for themselves
2. Structural pathology such as tumor previously ruled out using flexible laryngoscopy
3. Able to speak and read the English language
4. Failed a 2 month or longer trial of a proton pump inhibitor for the treatment of gastro-esophageal reflux
5. Women under 55 years of age who may become pregnant must have a negative pregnancy test and agree to barrier or hormonal methods of contraception during the study

Exclusion Criteria:

1. Active, untreated environmental allergies.
2. Smoking within past 5 years
3. Current upper respiratory infections
4. Use of narcotics (e.g. oxycodone, methadone) within the past week
5. History of amitriptyline use or other tricyclic antidepressants, pregabalin, gabapentin, baclofen, or other GABA analogues or inhibitors, for any medical conditions (not limited to chronic laryngitis) within the past 6 months
6. Use of any other monoamine oxidase inhibitors (MAOIs) other than amitriptyline

- within the past 4 weeks (selegiline, phenelzine, tranylcypromine, isocarboxazid, rasagiline, phenelzine sulfate, selegiline hydrochloride, rasagiline mesylate, tranylcypromine sulfate)
7. History of urinary retention
 8. History of an acute episode of a major depressive disorder within the past 12 months
 9. For women 18-55 years of age without history of menopause: currently nursing or pregnant, plans to become pregnant, or unwillingness to utilize contraception (barrier or hormonal methods)
 10. Currently participating in another clinical trial.

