For women who could potentially be pregnant (55 or younger and have not gone through menopause as determined by a medical provider), the physician will also explain that the effects of amitriptyline on the fetus during pregnancy are unknown, and that the patient cannot take the medication if she is pregnant or is nursing, plans to become pregnant, or is unwilling to use reliable contraception such as barrier or hormonal methods, if sexually active. Subjects known to be pregnant are not eligible to participate (and those who become pregnant will have to discontinue the medication), and all patients under the age of 55 who have not undergone menopause, as verified by a medical provider, will be required to undergo pregnancy testing at the Boston Medical Center patient laboratory before being eligible to receive medication.

If the patient chooses to join the trial, the physician will then discuss in detail all of the requirements of the trial, its potential benefits/risks, and its purpose. If the subject agrees to participate, he/she will be asked to sign and date the consent form. They will also be assigned a subject number. The consent will be signed during a regular clinic visit. Alternatively, patients may take the consent home and mail it back once they have decided to participate. The principle investigator will sign the consent when the subject returns it.

The subject will be informed that he/she will be started on either amitriptyline or placebo tablets taken at bedtime. The subject will then be randomized to amitriptyline or placebo in a 1:1 manner. Randomization of subjects will be managed by Boston Medical Center Investigational Pharmacy Services (IPS).

The starting dose will be 12.5mg nightly at bedtime. The dose may subsequently be increased by an additional 12.5mg tablet nightly every week if symptoms have not completely resolved, until either further increase is limited by side effects or a maximum

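### The only imputation method named is linear regression, which does not fit the patient's categorical overall rating; if draws are rounded, the arm difference usually shrinks modestly

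*Combined protocol and SAP*

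**What the plan says.** In the combined protocol and SAP, Analysis (efficacy and safety) sets out two approaches: "we will be performing both per-protocol and multiple imputation approach analyses". The imputation method follows: "Multiple imputation using the linear regression approach will be used to impute missing data, for subjects who do not complete treatment". The same paragraph explains that "subjects who drop out will not have any outcomes recorded", so a dropout lacks the overall rating as well as the questionnaire scores.

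The overall rating is described in two places. Study Design has: "A secondary outcome will be improvement in overall symptoms (yes/no), as subjectively assessed by patients". The secondary-outcome list in Analysis (efficacy and safety) has: "subjective report of whether symptoms are better, worse, or same after treatment". The post-treatment questionnaire described in Study Procedures names neither form; its only global item is percentage improvement.

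The plan gives no list of imputed outcomes, no list of predictors for the imputation model, no rounding rule, and no logistic, ordinal or multinomial imputation model.

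**The concern.** Linear-regression imputation adds a normal residual to a fitted mean, so it produces a continuous number. That suits the modified RSI total, which the plan treats as nearly continuous. It does not suit a yes/no or three-level answer, where essentially no draw equals a permitted value. An analyst following the text would have to analyse fractional values or round by a rule chosen later, possibly after seeing the data.

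The number of imputed values is not small. Study Design says "Thus, we anticipate a dropout rate during treatment of 30" percent, and multiple imputation is the only planned analysis that keeps the dropouts. Study Procedures also notes that the RSI, CSI and VHI-10 were not designed for chronic laryngeal neuropathy, which gives the patient's own overall verdict some added weight.

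**Working it through.** **Inputs from the plan.**
- Allocation: "The subject will then be randomized to amitriptyline or placebo in a 1:1 manner".
- Missing share *m*: 30% as stated. Analysis (efficacy and safety) also says "we expect to enroll 130 subjects in order for 100 to complete treatment", which implies 30/130 = 23%. At a true 30% loss, 100 completers need 100/0.70 = 143 enrolled, about 72 per arm. Both values of *m* are used.
- The plan has no figure for the categorical rating. Its one sample-size figure, 208 for the RSI (3.92/10.0, two-sided 0.05, 80% power), reproduces as 104 per arm with the t-test and is not in dispute here.

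**Assumptions.** Data are missing at random, and arm is in the imputation model. An active-arm rate of 56% is illustrative: it adds the 32% complete and 24% partial responses in the retrospective chart review of Table 1. The documents give no placebo rate for this outcome; 36% is assumed, and both rates are varied.

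**Yes/no, formula.** With arm rates p₁ and p₀, the pooled residual SD is s = √{[p₁(1−p₁) + p₀(1−p₀)]/2}. A draw in an arm with rate p is about N(p, s²). The chance of a draw outside 0–1 is Φ(−p/s) + 1 − Φ((1−p)/s). Rounding at 0.5 gives an imputed rate of Φ((p−0.5)/s). The overall difference is (1−m) × true difference + m × imputed difference.

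**Yes/no, 56% vs 36%.**
- s = √[(0.2464 + 0.2304)/2] = 0.488.
- Draws outside 0–1: 31% (active) and 33% (placebo).
- Rounded rates: Φ(0.06/0.488) = 0.549 and Φ(−0.14/0.488) = 0.387. The difference is 0.162 among imputed subjects, against a true 0.200.
- Overall at m = 30%: 0.7 × 0.200 + 0.3 × 0.162 = 0.188, a loss of 1.2 points (about 6%).
- Overall at m = 23%: 0.191, a loss of 0.9 points.
- Simulation (72 per arm, 30% missing, 20 imputations, 1,500 repeats): completers 0.198, unrounded 0.198, rounded 0.186.

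**Yes/no, other rates at m = 30%.**

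| True rates | True difference | Rounded, overall |
|---|---|---|
| 70% vs 30% | 0.400 | 0.381 |
| 56% vs 20% | 0.360 | 0.342 |
| 45% vs 25% | 0.200 | 0.188 |
| 95% vs 80% | 0.150 | 0.133 |
| 87% vs 8% | 0.790 | 0.794 |

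The last row uses the rates of the amitriptyline versus codeine/guaifenesin trial in Table 1 (13/15 and 1/13). There is no shrinkage there.

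**Three levels** (worse = 0, same = 1, better = 2; cut-points 0.5 and 1.5; this coding is an assumption). With arm mean μ and pooled SD s, the imputed *better* rate is 1 − Φ((1.5 − μ)/s).

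Worked case: active 10/34/56 and placebo 10/54/36 (percent worse/same/better). The means are 1.46 and 1.26, and s = √[(0.4484 + 0.3924)/2] = 0.648. The imputed *better* rates are 0.475 and 0.356, a difference of 0.120. Overall: 0.7 × 0.200 + 0.3 × 0.120 = 0.176.

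| Active (worse/same/better) | Placebo | True difference in *better* | Overall, m = 30% | Loss, points |
|---|---|---|---|---|
| 10/34/56 | 10/54/36 | 0.200 | 0.176 | 2.4 |
| 5/35/60 | 15/45/40 | 0.200 | 0.194 | 0.6 |
| 20/20/60 | 30/30/40 | 0.200 | 0.182 | 1.8 |
| 10/20/70 | 16/50/34 | 0.360 | 0.325 | 3.5 |
| 5/25/70 | 10/60/30 | 0.400 | 0.369 | 3.1 |

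The result depends on the assumed share reporting *worse*. An active arm with 70% *better* is imputed at 56% when 10% report *worse*, at 60% when 5% do, and at 67% when none do (placebo arms 16/50/34, 10/60/30 and 0/70/30).

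**Scale.** With 50 completers per arm at 56% vs 36%, the standard error of the difference is √(0.56 × 0.44/50 + 0.36 × 0.64/50) = 0.098, or about 10 points. The losses above are a fraction of one standard error.

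**The case against.** The strongest objection is that the shrinkage comes from rounding, a step the plan does not contain. For a yes/no item the arm rate is the mean of a 0/1 variable, so unrounded draws give the difference directly and without bias, as the simulation confirms. This stands. A reader might infer that the imputed analysis is necessarily biased toward no difference; the documents do not support that.

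Nor is there a general rule that the better arm is pulled down. At 45% vs 25% the better arm is imputed slightly up, at 45.7%. The difference still shrinks, because the other arm rises further, to 29.6%. At 87% vs 8% it does not shrink at all.

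Three further points stand in part:
- The imputation sentence is followed at once by the primary outcome definition, and the sponsor may have meant it for scores only. In that case the overall rating has no stated imputation method, and the same clarification is needed.
- The yes/no and better/worse/same descriptions may be one survey item. A reader might count two affected outcomes; the text does not establish that. One categorical outcome remains either way.
- The scores and percent improvement are bounded too, so out-of-range draws alone do not condemn linear imputation. The stronger ground is that a three-level answer has to be tabulated, and fractional draws cannot be.

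**Conclusion.** The point holds as a mismatch between method and outcome, of minor weight. As written, the plan applies a continuous-data method to a categorical rating and leaves open how the draws become answers. About a third of yes/no draws fall outside 0–1 (25% to 44% by arm across the rates tried).

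If the draws are rounded, the overall difference usually falls by about 1 to 2 points for yes/no. For *better* it falls by about 2 to 4 points in most settings tried, and by 0.6 in one. These sizes rest on 30% missing at random, arm in the imputation model, 0/1/2 coding and assumed response rates; at 23% missing they are smaller. The primary modified RSI analysis and all per-protocol results are unaffected.

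**What to change.** In Analysis (efficacy and safety), keep linear regression for the modified RSI total, VHI-10, CSI and percent improvement. Add that the overall rating will be imputed by logistic regression if it is yes/no, or by ordinal logistic regression if it is better/same/worse, with treatment arm and baseline as predictors. Naming arm matters in its own right: in the simulation, leaving it out cut a 20-point difference to about 14, with or without rounding. The same place should say whether the eleven individual symptom items are imputed separately.

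Reconcile Study Design, the secondary-outcome list and the post-treatment questionnaire in Study Procedures on whether the overall rating is one item or two, and on its scale.

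The cost is one sentence plus that reconciliation, with no new data or visits. The downside is that an ordinal model can be unstable if few subjects report *worse*. Any merging of levels should therefore be fixed before unblinding.

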The treatment assignment will not be available to the clinical staff that will administer the study questionnaires and analyze resulting data while subjects are receiving the study drug or placebo, except in case of severe adverse side effect or other emergency requiring urgent unblinding. If emergency unblinding is required as noted by the PI or study staff, they will contact the IPS on-call personnel who will have access to the randomization table.

On Days 7, 14, 21, 28, 35, 42, 49, and 56 of the study the subject will be contacted by phone by a blinded study coordinator. The subject will be asked about side-effects and concerns, and confirm the dose they are taking that week. The study coordinator will relay any medical concerns to the primary investigator for consideration and follow-up, or to the nearest emergency department if the issue is too urgent to wait. The study staff will instruct the subject to remain at the same dose, increase the dose by 1 capsule or discontinue the study drug in accordance with the protocol. The subject will also be encouraged to contact the study coordinator both before and after the scheduled phone

calls and initial visits if they experience any adverse events or have additional concerns.

The subject will be instructed to discontinue taking all capsules after 8 weeks, regardless of the number of capsules remaining or any improvement experienced on the capsules. No tapering is required prior to stopping treatment.

At the time of enrollment, at the initial study visit, the subject will also be scheduled for an in-office follow-up 8 weeks after starting the capsules (as is standard of care for the treatment of chronic laryngitis). At this visit the subject will be asked to fill out a post-treatment questionnaire including a repeat modified RSI, CSI, VHI-10, and reported overall subjective percentage improvement from baseline. The latter will serve as a separate independent variable, given that neither the RSI, CSI, nor VHI-10 were specifically designed to evaluate chronic laryngeal neuropathy. Any questions the subject might have regarding the questionnaires are answered by the PI.

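### The stated reason for ruling out intention-to-treat does not hold, and the plan neither ranks its two analyses nor says how off-drug 8-week scores are used

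*Combined protocol and SAP*

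**What the plan says.** On missing data, the section Analysis (efficacy and safety) makes three statements:

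- Analyses: "we will be performing both per-protocol and multiple imputation approach analyses". Neither is called primary, and the per-protocol set is not defined.
- Imputation: "Multiple imputation using the linear regression approach will be used to impute missing data, for subjects who do not complete treatment".
- Intention-to-treat: "Intention-to-treat analysis is not possible, since our outcomes are determined by the 8 week post-treatment survey", with the added reason that "there are no intermediate data points with regards to treatment efficacy outcomes" and that those who drop out will have no recorded outcome.

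Study Design and the Analysis section both specify an ANCOVA of the 8-week modified RSI adjusted for baseline, but name no analysis population. Study Design sets a two-sided level of 0.049 for the final analysis.

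Two other places bear on who has an 8-week score. Under Study Design, for subjects who withdraw from treatment because of adverse events, "we will ask that they continue coming in for follow-up visits and finish the remaining parts of the visits off the study drug". Under Study Procedures, at enrolment "the subject will also be scheduled for an in-office follow-up 8 weeks after starting the capsules", and "At this visit the subject will be asked to fill out a post-treatment questionnaire including a repeat modified RSI".

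On the amount of dropout: "With a dropout rate of 30%, we expect to enroll 130 subjects in order for 100 to complete treatment".

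**The concern.** Having only one outcome time, and some missing scores, is a missing-data problem. It does not stop anyone analysing all randomised subjects in their assigned arm. The baseline modified RSI, CSI and VHI-10 are collected at the first study visit, so there are predictors to impute from.

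Three things are then left open: which of two analyses decides the trial, who belongs in the per-protocol set, and whether a score observed after a subject stopped drug is used, left out or replaced by an imputed value. The two analyses can disagree, and a choice made after the results are known would weaken any conclusion. If observed off-drug scores are left out, the comparison is no longer of the groups as randomised. Imputing from arm and baseline does not repair that when dropout depends on the outcome.

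**Working it through.** **1. The plan's own figures.** An effect size of 0.392 (3.92/10), two-sided 0.05 and power 0.8 give 103.1 per arm by the two-sample t-test, so 104 per arm and 208 in total. This matches the plan; the point disputes no sample-size figure.

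**2. Amount of dropout.** Enrolling 130 for 100 completers implies 30/130 = 23% dropout. The stated rate is 30%, or 0.30 × 130 = 39 subjects. Both are carried below.

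**3. How many off-drug scores the plan asks for.** Three pilot subjects cited adverse events, against 5 + 5 = 10 who dropped out after starting treatment. If that share applies (assumption), about 0.3 × 39 ≈ 12 subjects would be asked back for an off-drug score and about 27 would not.

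**4. Simulation.** From the documents: SD 10, true difference 0 or 3.92, 130/2 = 65 per arm, two-sided 0.049. Assumed: baseline correlation 0.5; returners are a random subset of dropouts; completer ANCOVA stands in for the undefined per-protocol analysis. Multiple imputation draws from a regression on arm and baseline modified RSI, with 20 imputations combined by Rubin's rules.

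*Random dropout, 23% to 30%:*

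| Imputation analysis | Either significant, no effect | The two disagree, true 3.92 |
|---|---|---|
| Imputes all dropouts | about 5% to 6% | about 4% to 9% |
| Uses returned scores from 30% of dropouts | about 6% to 7% | about 10% to 13% |

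*No drug effect, dropout on amitriptyline correlated 0.3 to 0.5 with a worse 8-week score, placebo dropout random:*

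| Dropout | Completer ANCOVA: bias toward drug | Imputing all dropouts from arm and baseline | Using a returned 30% |
|---|---|---|---|
| 23% | 0.9 to 1.5 points | the same | about 0.5 to 1.0 |
| 30% | 1.1 to 1.9 points | the same | about 0.6 to 1.2 |

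The error rate is about 7% to 19% for the first two analyses and about 6% to 10% with returned scores. The sign reverses if only placebo dropout is outcome-related. If the two arms are alike, bias is about 0 and error about 5%.

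**5. Tipping example (imputation variance ignored).** With n observed scores per arm and baseline correlation ρ, the smallest significant difference is t(0.9755, 2n − 3) × 10 × √(1 − ρ²) × √(2/n). The shift in imputed amitriptyline scores that removes significance is (3.92 − threshold) / fraction missing.

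- ρ = 0.5, 23% missing, n = 50: threshold 3.45; shift (3.92 − 3.45)/0.23 ≈ 2.0 points.
- ρ = 0.5, 30% missing, n = 45 to 46: threshold 3.65 to 3.60; shift (3.92 − 3.65)/0.30 = 0.9 to (3.92 − 3.60)/0.30 ≈ 1.1 points.
- ρ = 0.3, 30% missing: threshold 4.02 to 3.97, so 3.92 is not significant to begin with.

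**The case against.** The strongest reply is that the dispute is largely about a label. Imputing for non-completers is already close to an as-randomised analysis, and deleting one sentence changes no estimate by itself. Imputing only missing data would also naturally leave observed scores as they are. That is a reasonable reading, but the imputation sentence can equally be read as covering everyone who stops treatment, and the plan does not choose. Nothing in the documents answers the missing ranking or the undefined per-protocol set.

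A reader might infer that the protocol flatly contradicts itself, since one section says dropouts have no outcomes and another asks some of them back. The documents do not support that: those who drop out can be read as those who never complete the survey. The fault is silence about off-drug scores.

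A reader might also infer that the planned analyses are biased toward drug. This is not shown either. Pilot dropout was 5 versus 5, and adverse events were cited by two subjects on placebo and one on amitriptyline. The bias figures need outcome-related dropout in one arm only. The gain from returned scores also assumes that returners are a random subset, which volunteers may not be.

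Finally, the request to return covers adverse-event withdrawals only. A 30% return rate therefore needs nearly all of them to attend, and a higher rate has no basis in the current text.

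**Conclusion.** The concern holds. The reason given for ruling out intention-to-treat is wrong, no primary analysis is named, the per-protocol set is undefined, and the use of off-drug scores is unstated.

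The practical weight lies in disagreement between two unranked analyses and in the unspecified handling of off-drug scores. Inflation of the error rate from having two analyses is small, so it would be too strong to say that they materially break control of the 0.049 level. Bias is possible and conditional. All sizes rest on SD 10 and 65 per arm, on an assumed baseline correlation of 0.5 (0.3 in the last tipping line), and on the dropout mechanisms stated with them.

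This should be fixed, as a cheap improvement.

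**What to change.** In the Analysis section, delete the sentence calling intention-to-treat impossible and state:

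> The primary analysis includes all randomised subjects in their assigned arm. It is the planned ANCOVA of the 8-week modified RSI adjusting for baseline, using every observed 8-week score whether or not the subject was still taking study drug. Only missing 8-week scores are imputed, by linear-regression multiple imputation using arm and the baseline modified RSI, CSI and VHI-10. The per-protocol set is defined before unblinding and that analysis is supportive.

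Do not impute from last recorded dose. Under Study Procedures the dose may rise weekly while symptoms persist, so a low last dose can mean resolution in a completer and merely early stopping in a dropout. In illustrative no-effect simulations with random but unequal dropout (for example 40% versus 20%), adding it created about 0.4 to 1.0 points of bias toward amitriptyline, against about 0 without it.

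Also:

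- In Study Design, extend the request for the 8-week questionnaire to everyone who stops study drug for any reason, with a phone option for those who cannot attend. Report off-drug scores per arm.
- State that the interim trigger and the target count subjects with an observed 8-week score, and that the interim uses the same analysis rule. Both are now worded in terms of completers, so this settles whether off-drug returners count.
- If the Wilcoxon fallback is used, say that it covers only subjects with observed scores, on or off drug.
- Optional: a delta-adjusted sensitivity analysis, by arm.

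The cost is wording and some follow-up effort, since the visit is already scheduled for every subject. The downsides are that the estimate may be smaller, phone scores differ in mode from the in-office form, and off-drug scores may reflect other treatment, which should be recorded. Bias is reduced, not removed. The on-drug question stays available through the per-protocol analysis.
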